## 2.9 Statistical Methods

Unless specified otherwise, SAS® Version 9.0 or higher will be utilized to perform the statistical analyses of efficacy and safety measures.

Categorical variables will be summarized in general using frequencies and percentages, whereas continuous variables will be summarized in general using descriptive statistics of number of observations (n), mean, standard deviation (SD), minimum (Min), median, and maximum (Max).

In both data listings and CRF domain data tabulations, subject ID will consist of site number plus the subject screening number in the format of XXX-YYY, where XXX denotes the site number and YYY the subject's screening number within the site.

Hypothesis testing, unless otherwise indicated, will be performed at the 5% significance level. All p-values will be rounded to four decimal places; p-values less than 0.0001 will be presented as '<0.0001' in all tables. All group comparisons from analysis of variance (ANOVA) and/or analysis of covariance (ANCOVA) models will be based on Type III sums of squares. In the case of substantial non-normality, results from non-parametric tests will also be reported. All confidence intervals (CI) will be two-sided with 95% coverage, unless stated otherwise.

### 2.9.1 Primary efficacy analysis

The primary efficacy endpoint for this study is the proportion of subjects with anesthetic effect that is adequate for eye exam as assessed by the PI at 2-4 minutes post application of the dose. The definition of the primary efficacy endpoint is given in [Section 2.6.1](#). The non-parametric Cochran-Mantel-Haenszel (CMH) test with adjustment for study eye side will be used to examine the difference and/or therapeutic equivalence in proportion of subjects with anesthetic effect at 2-4 minutes post dose between the active treatment group and active-control group.

In primary efficacy analysis, rather than to reject the null hypothesis when there is a difference ( $P \leq 0.05$ ) between AG-920 and active-control treatments, this study is designed to accept the null hypothesis that there is no difference in anesthetic effect between AG-920 and active-control treatments ( $P > 0.05$ ), indicating the therapeutic equivalence of AG-920 to Proparacaine without reference to a pre-defined non-inferiority margin.

To further measure the therapeutical equivalence of anesthetic effect of AG-920 to the active-control treatment, between-group difference and its 95% confidence interval (CI) as well as its 90% CI in the proportion of subjects with anesthetic effect (yes=1) vs. non-effect (no=0) will be calculated using a two-way analysis of variance (ANOVA) model with treatment (the effect of interest) and study eye side as the effects. The study-eye-side effect is used as a blocking factor in the model to control the potential treatment differences among the study eye sides. The conventional 90% CI of the between-group difference will be used to measure the extent of the equivalent margin or non-inferiority margin of anesthetic effect of AG-920 to Proparacaine. The conventional rule of the 90% CI of the between-group difference lying

within +/-20% of the reference treatment will be employed to claim the therapeutic equivalence or non-inferiority of AG-920 to Proparacaine.

The primary efficacy analysis will be performed for the ITT population, which will include all randomized subjects who received the complete application of one study dose (i.e., two drops). The analysis model adjusts for the effect of the study eye side. The study-eye-side by treatment interaction will be examined through the summary descriptive statistics of subjects with anesthetic effect for each study eye side.

Prior to the determination of the primary efficacy variable, handling of missing values that occur prior to eye exam is described in [Section 2.8](#).

The primary efficacy endpoint will also be analyzed for the PP population as well as for subgroups of the ITT population, such as male vs. female, Caucasian vs. Non-Caucasian, age groups, and iris color dark brown vs. other colors.

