## 9 Statistics

### 9.1 Primary Hypotheses

H01: The percentage of subjects with positive outcomes is NOT different between subjects treated with AG-920 and Proparacaine.

H11: The percentage of subjects with positive outcomes is different between subjects treated with AG-920 and Proparacaine.

The primary hypotheses outlined above are based on a controlled trial design for superiority of testing. The current study has an active-control treatment with the intention to compare the treatment of AG-920 in reference to the active-control treatment of Proparacaine, rather than testing for superiority against the latter.

The experimental hypothesis of this study focuses thus on the primary null hypothesis (H01) outlined above and intends, for simplicity, to accept the null hypothesis (H01) without a pre-defined non-inferiority margin should the null hypothesis (H01) is NOT rejected at a statistically significant level of 0.05 (2-sided).

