### 9.4 *Statistical methods to be employed*

#### 9.4.1 **General Considerations**

All continuous study assessments will be summarized by treatment and time point (as applicable) using descriptive statistics (n, mean, median, standard deviation, minimum, and maximum). All categorical study assessments will be summarized by treatment and time point (as applicable) using frequency counts and percentages.

Hypothesis testing, unless otherwise indicated, will be performed at a two-sided 0.05 significance level. Where applicable, two-sided 95% confidence intervals will be reported. All p-values will be displayed to four decimal places, with p-values less than 0.0001 presented as '<0.0001' and p-values greater than 0.9999 presented as '>0.9999'. Difference between Articaïne Sterile Topical Ophthalmic Solution (AG-920) and Proparacaine will be calculated as Articaïne Sterile Topical Ophthalmic Solution – Proparacaine, with the 95% CI of the difference being reported for the reference of the treatment therapeutical equivalence.

All study data will be listed by treatment, subject, time point, and eye (as applicable).

Statistical methods will be more fully described in a separate document (Statistical Analysis Plan).

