### 9.4.6 Analysis of Efficacy

Analyses will be performed primarily on the ITT population and will be repeated on the PP population to determine robustness of results. For the primary efficacy endpoint of the proportion of subjects in whom there was adequate local anesthetic effect to perform an eye exam for which the subject is seeing the ophthalmologist, a Pearson chi-square test will be used for the comparison of the two proportions from the two treatment groups. In addition, a two-sided 95% confidence interval for the difference in response rates between the two treatment groups will be calculated. If the difference in response rates is around zero and the *P* value is NOT statistically significant (i.e.,  $P > 0.05$ ), then the therapeutical equivalence of AG-920 to the Proparacaine will be claimed, without reference to a pre-defined non-inferiority margin. The 95% CI of the difference in response rates will be reported to measure the extend or margin of the efficacy equivalence of AG920 to Proparacaine.

Sub-group analyses based upon pre-study characteristics such as sex, iris color, age, and race may be completed to further investigate the efficacy and safety measures.

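### The single efficacy claim has two unranked decision rules: P > 0.05 with no margin (Protocol 9.1, 9.4.6 and SAP 2.9.1) and a 90% CI within ±20% (SAP 2.9.1 only)

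*SAP*

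**What the plan says.** **P rule.** Protocol 9.1 sets up a null hypothesis of no difference and "intends, for simplicity, to accept the null hypothesis" if it is not rejected at two-sided 0.05. Protocol 9.4.6 opens with a condition, "If the difference in response rates is around zero", adds that P must exceed 0.05, and concludes: "then the therapeutical equivalence of AG-920 to the Proparacaine will be claimed, without reference to a pre-defined non-inferiority margin". No number is attached to that first condition. SAP 2.9.1 repeats the rule: "this study is designed to accept the null hypothesis that there is no difference in anesthetic effect between AG-920 and active-control treatments". It takes P > 0.05 as indicating equivalence, again without a margin.

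**CI rule.** The next paragraph of SAP 2.9.1 begins "To further measure the therapeutical equivalence of anesthetic effect of AG-920 to the active-control treatment" and calculates a difference with 95% and 90% CIs from a two-way ANOVA on the 0/1 outcome, with treatment and study eye side as effects. It then says that a 90% CI lying "within +/-20% of the reference treatment will be employed to claim the therapeutic equivalence or non-inferiority of AG-920 to Proparacaine".

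**The protocol has no CI rule.** Protocol 9.4.1 provides a 95% interval, "with the 95% CI of the difference being reported for the reference of the treatment therapeutical equivalence", with no threshold. It leaves fuller methods to the SAP but does not say which document prevails if they differ.

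**Sample size.** Protocol 9.2 plans up to 70 children randomized 1:1 to give at least 60 evaluable. The number was directed by the regulator and was not derived from a margin.

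**The concern.** The two rules answer different questions. A P value above 0.05 says only that the data do not exclude zero difference, and the smaller the trial, the easier that is to achieve. A CI inside a margin says that the data exclude a difference larger than the margin. Only the second supports an equivalence claim with a controlled chance of being wrong.

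Both rules are written as sufficient for the claim, so the same data can be called equivalent under one and not shown under the other. Protocol 3.5 masks only subjects and their parents or guardians, so site staff know the allocation. A choice between rules that is left open could be made with results in view.

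The CI rule also leaves two matters undefined: whether the claim is two-sided equivalence or one-sided non-inferiority, and whether 20% means percentage points or 20% of the Proparacaine rate.

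**Working it through.** **Inputs.** From the documents: 30 per arm (60 evaluable) and 35 per arm (70 randomized), two-sided α of 0.05, 90% CI, ±20%. The plan contains no power calculation to reproduce. All response rates below are assumptions.

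**Formulas.** With n per arm, observed rates pA (AG-920) and pP (Proparacaine), d = pA − pP and pooled rate p̄:

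- P rule: Pearson χ² = d² / [p̄(1 − p̄)·2/n], 1 df, no continuity correction. An undefined χ² counts as not significant.
- CI rule: d ± t(0.95, 2n − 3)·√(s²·2/n), where s² = [n·pA(1 − pA) + n·pP(1 − pP)]/(2n − 3). This is the SAP's ANOVA interval with eye side balanced and without effect. At n = 30, t = 1.672.

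**One trial, two answers.** AG-920 26/30, Proparacaine 29/30, d = −0.100.

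- p̄ = 55/60 = 0.9167. χ² = 0.0100/(0.9167 × 0.0833 × 2/30) = 0.0100/0.00509 = 1.96, P = 0.16. The P rule claims equivalence.
- s² = (3.467 + 0.967)/57 = 0.0778. SE = √(0.0778 × 2/30) = 0.0720. The 90% CI is −0.100 ± 1.672 × 0.0720, or −22.0 to +2.0 points. The CI rule does not.

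A starker case is 21/30 vs 27/30: P = 0.053, so the P rule claims equivalence, with a 90% CI of −37.2 to −2.8 points.

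**False claims under a true 20-point deficit.** Every possible outcome table (31 × 31 or 36 × 36) was weighted by its binomial probability. The CI rule is read as ±20 points, two-sided.

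| True Proparacaine vs AG-920 | P rule, n=30 | CI rule, n=30 | Rules disagree, n=30 | P rule, n=35 | CI rule, n=35 | Rules disagree, n=35 |
|---|---|---|---|---|---|---|
| 80 vs 60% | 61% | 1% | 59% | 55% | 2% | 52% |
| 90 vs 70% | 50% | 4% | 46% | 44% | 5% | 38% |
| 95 vs 75% | 37% | 7% | 30% | 30% | 6% | 24% |
| 99 vs 79% | 18% | 10% | 8% | 12% | 7% | 5% |
| 100 vs 80% | 12% | 12% | 0% | 6% | 6% | 0% |

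If both true rates are 90%, the rules disagree in 28% of trials (n = 30) or 22% (n = 35).

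**Effect of the protocol's unquantified condition.** If it meant an observed difference within 10 points (an assumption), P > 0.05 plus that limit gives false claims in 23/20/17/14/12% at n = 30 and 17/14/11/7/6% at n = 35, in table order.

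**Direction of disagreement.** With equal arms, all 54 CI-passing tables at n = 30 and all 90 at n = 35 also pass P. Accepting either rule is then the same as using P alone, and requiring both is the same as using the CI alone. Unequal arms allow rare exceptions: 25/28 vs 35/35 has P = 0.047 and a 90% CI of −19.7 to −1.8.

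**Ambiguities inside the CI rule.**

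- Scale: 26/30 vs 28/30 has a 90% CI of −19.9 to +6.5. It passes ±20 points but fails 20% of the reference, since 0.20 × 93.3% = 18.7 points.
- Direction: 30/30 on AG-920 vs 25/30 has P = 0.020 and a 90% CI of +5.0 to +28.3. It is non-inferior, but fails both two-sided equivalence and the P rule.

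**Eye-side adjustment.** Exact enumeration of the SAP's stratified test and ANOVA, with no true eye-side effect, moves the P and ANOVA figures by at most 0.5 point at n = 30 and 1.7 points at n = 35.

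**The case against.** - **The SAP leans towards the CI rule.** Its P > 0.05 only indicates equivalence, while its CI is what will be used to claim it, and the protocol defers detail to the SAP. If the CI rule governs, or both rules are needed, most of the harm goes. This has weight but does not settle the matter. Protocol 9.4.6 also says that equivalence will be claimed on its own rule, the SAP keeps the P rule, and its lead-in presents the CI as a further measure.
- **Protocol 9.4.6 asks for more than P > 0.05.** This is correct. However, the extra condition has no number and is absent from Protocol 9.1 and SAP 2.9.1. Even with a 10-point limit, false claims remain at 12–23% at 30 per arm.
- **Response may be near the ceiling.** Both documents describe topical agents such as Proparacaine as giving excellent surface anesthesia, and Protocol 4.1 requires children judged able to undergo an eye exam. If both true rates are 98%, the rules disagree in only 0.2% of trials at 30 per arm. This limits the practical size, but neither document states an expected rate.
- **Choosing the CI rule does not cure everything.** This stands. At 100 vs 80% both rules give 12% false claims at 30 per arm, and only a different interval method lowers that.
- **Text is redacted.** SAP 2.1 and 2.5 are partly blacked out and may hold a reason for 20%. A ranking of the rules could also be hidden, so the finding is limited to the readable text. The contradiction itself is readable in both documents.

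**Conclusion.** The concern holds and must be fixed. For its only efficacy conclusion, the plan states one rule with no margin and another with a ±20% margin, and no readable passage ranks them. If P > 0.05 alone suffices, the false-claim rate is uncontrolled: 37–61% at 30 per arm and 30–55% at 35, for a true 20-point deficit at assumed Proparacaine rates of 80–95%. It falls to 12% and 6% at 100%, where the two rules coincide. These figures assume equal arms, no eye-side effect and the ±20-point two-sided reading. Under the relative reading, disagreement with both true rates at 90% rises from 28% to 45% at 30 per arm. The size depends on response rates that the documents do not give; the contradiction does not.

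**What to change.** 1. Remove the acceptance of the null on P > 0.05 from Protocol 9.1 and 9.4.6 and SAP 2.9.1, together with the unquantified closeness condition in Protocol 9.4.6. Restate the hypotheses in Protocol 9.1 in terms of the margin.
2. Make the SAP's 90% CI rule the only decision rule, worded identically in both documents. Report P as descriptive.
3. State whether the claim is two-sided equivalence or one-sided non-inferiority, and whether 20% is in percentage points or relative to the Proparacaine rate. Give the reason for 20% unless the redacted text already does.
4. Do this before anyone reviews outcomes by treatment, and at the latest before treatment assignment is merged into the database (the step named in SAP 3.1).

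**Cost.** No change to data collection, but a protocol amendment under Protocol 12.4 and a SAP revision. The claim also becomes harder to reach. Probability of a claim when the arms are truly equal:

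| Rule | Both 95%, n=30 | Both 90%, n=30 | Both 95%, n=35 | Both 90%, n=35 |
|---|---|---|---|---|
| P > 0.05 | 97% | 95% | 96% | 94% |
| CI, ±20 points, two-sided | 92% | 66% | 93% | 73% |
| CI, 20% of reference, two-sided | 86% | 49% | 90% | 58% |
| CI, −20 points, one-sided | 96% | 83% | 97% | 86% |

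**Optional refinement, not part of the must-fix.** The ANOVA interval on 0/1 data is somewhat liberal near the ceiling: 7–12% false claims at 30 per arm and 6–7% at 35, for Proparacaine rates of 95–100%. At 80–90% it is not inflated (1–5%). A score interval stratified by eye side, such as stratified Miettinen-Nurminen, gives 4.4% and 4.5–6.1% at the high rates. It keeps the SAP's adjustment ("The study-eye-side effect is used as a blocking factor in the model"). Its price is a lower chance of a claim with truly equal arms: 80% (both 95%) or 53% (both 90%) at 30 per arm, and 88–89% or 65–66% at 35.

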### 2.5 Sample Size Estimation

This study has an active-control treatment with the intention to compare the treatment of AG920 in reference to the active-control treatment of Proparacaine in healthy pediatric subjects in order to meet the regulatory requirements, rather than testing for superiority against the latter.

The study plans to randomize approximately 70 subjects in order to have at least 60 evaluable subjects, in a 1:1 allocation ratio for AG-920 and reference groups. [REDACTED]

[REDACTED]

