## **2.8 Handling of Missing, Incomplete, and Repeat Data**

For efficacy parameters, missing or invalid data for anesthetic effect assessment will be assessed for each subject post dose. Missing values due to either invalid data or early termination will be considered as NO anesthetic effect for the subject.

For safety parameters, missing or invalid data will be treated as missing for the corresponding assessment of a visit.

All data records are identified by study visit and/or assessment time point. Should repeated data records exist within a study visit and/or assessment time point, the first valid data record will be utilized for any statistical analyses of the corresponding study visit and/or assessment

time point. All existing data records including the repeat data records in the study database will be presented in data listings and CRF data tabulations.

Any resultant incomplete or missing data of either efficacy or safety parameters will be treated as missing in the statistical analyses involving these parameters.

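### The equivalence interval is a normal-theory ANOVA interval on a yes/no outcome: it is [0, 0] if every child responds, and its false-claim rate exceeds 5% when control response is about 95% or more

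*SAP*

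**What the plan says.** SAP 2.9.1 codes the primary outcome as 1 (effect) or 0 (no effect). The between-group difference and its 95% and 90% intervals "will be calculated using a two-way analysis of variance (ANOVA) model with treatment (the effect of interest) and study eye side as the effects". The 90% interval has two jobs. One is descriptive: "The conventional 90% CI of the between-group difference will be used to measure the extent of the equivalent margin or non-inferiority margin". The other is decisional: the 90% interval lying "within +/-20% of the reference treatment will be employed to claim the therapeutic equivalence or non-inferiority of AG-920 to Proparacaine".

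No score, exact or other binomial interval is named. The general text in SAP 2.9 offers only this: "In the case of substantial non-normality, results from non-parametric tests will also be reported". That adds tests and supplies no replacement interval.

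Protocol 9.4.6 also asks for a 95% interval, which "will be reported to measure the extend or margin of the efficacy equivalence of AG920 to Proparacaine", but names no method for it.

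On size, SAP 2.5 plans to "randomize approximately 70 subjects in order to have at least 60 evaluable subjects", allocated 1:1. On missing outcomes, SAP 2.8 states: "Missing values due to either invalid data or early termination will be considered as NO anesthetic effect for the subject".

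**The concern.** An ANOVA interval estimates one residual variance for both arms and uses a t quantile. A 0/1 outcome has variance p(1 - p), which shrinks to zero as p approaches 1. Two problems follow.

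- **No failures.** The estimated variance is zero, so the interval has no width. The CMH and Pearson statistics are undefined too, so the primary table would show no P value beside an interval implying perfect knowledge from 60 to 70 children.
- **One arm at or near 100%, the other lower.** The interval is too short on the side facing the margin, so equivalence can be claimed too often when AG-920 is truly 20 points worse.

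A high response rate is a reasonable planning case. The protocol introduction describes topical agents such as proparacaine as giving excellent surface anesthesia, and inclusion criterion 2 requires children capable of an eye exam. Neither document gives a figure in the visible text.

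**Working it through.** The plan states no power or error rate to reproduce. The benchmark is the 5% per side implied by a 90% interval.

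**Inputs.** From the documents: 0/1 outcome, ANOVA on treatment and eye side (residual df = N - 3), 90% interval, +/-20 margin, 30 to 35 per arm. Assumed: the margin means absolute points (the relative reading is in step 5), and control rates range from 80% to 100%.

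**1. Every child responds.** Residual sum of squares = 0, so SE = 0 and both intervals are [0, 0]. For the Miettinen-Nurminen interval with n of n in both arms, the constrained estimates at difference -d are 1 - d and 1. The limit then solves z² = d(2n - 1) / [2(1 - d)].
- n = 30, 90% (z² = 2.706): d/(1 - d) = 5.411/59 = 0.0917, so d = 8.4 points. For 95% (z² = 3.841), d = 11.5.
- n = 35: 7.3 (90%) and 10.0 (95%).

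The chance that all respond is p^N. At p = 99, 98, 97, 95% it is 55, 30, 16, 5% for N = 60 and 49, 24, 12, 3% for N = 70 (for example 0.98^60 = 0.298). At 98%, exactly one failure in 60 is likelier: 60 x 0.02 x 0.98^59 = 0.364.

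**2. False-claim rate at a true 20-point deficit.** The case of 100% control and 30 per arm can be done by hand.
- 27/30 vs 30/30: SSE = 27 x 3/30 = 2.7; MSE = 2.7/57 = 0.0474; SE = sqrt(0.0474 x 2/30) = 0.0562; half-width = 1.672 x 0.0562 = 0.0940. The interval is -19.4 to -0.6: claimed.
- 26/30 vs 30/30: SSE = 26 x 4/30 = 3.467; half-width 0.1065; lower limit -24.0: not claimed.
- ANOVA therefore claims at 27 or more: P(Bin(30, 0.8) >= 27) = 12.3%. The score interval needs 28 or more: 4.4%.
- At 35 per arm both methods need 32 or more, so both give 6.1%.

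Full enumeration of outcomes (eye side omitted, df N - 3, unstratified score), false-claim rate in %:

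| Control rate | ANOVA, 30/arm | Score, 30/arm | ANOVA, 35/arm | Score, 35/arm |
|---|---|---|---|---|
| 100% | 12.3 | 4.4 | 6.1 | 6.1 |
| 98% | 9.1 | 5.2 | 6.6 | 4.6 |
| 95% | 7.0 | 4.8 | 6.1 | 4.6 |
| 92% | 5.3 | 4.3 | 5.6 | 4.5 |
| 90% | 4.3 | 3.8 | 5.1 | 4.4 |
| 85% | 2.5 | 2.8 | 3.6 | 4.1 |
| 80% | 1.4 | 2.3 | 2.4 | 3.1 |

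**3. With eye side in the model.** Simulation with each child's eye randomized 50:50 gives, at control 100/98/95/90%, 11.3, 8.5, 6.4, 4.4% at 30 per arm and 7.2, 7.0, 6.0, 4.9% at 35. Enumeration with near-balanced eyes and equal arms of 31 to 34 gives 5.5% to 6.5% at 95% control.

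**4. Results where the decision changes.**
- 27/30 vs 30/30: ANOVA -19.4 to -0.6 (claimed); score -22.7 to -1.2 (not claimed). This depends on eye allocation. With right eyes 17 vs 13 and failures split 1 right, 2 left, ANOVA gives -20.1 to -1.2 (not claimed).
- 31/35 vs 34/35, eye side omitted: SSE = 31 x 4/35 + 34 x 1/35 = 4.514; MSE = 4.514/67 = 0.0674; SE = 0.0620; half-width 0.1035. ANOVA is -18.9 to +1.8 (claimed); score is -20.85 to +2.03 (not claimed).

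**5. Margin read as 20% of the observed control rate.** At control 90/95/98/100%, ANOVA gives 3.1, 5.9, 8.8, 12.3% at 30 per arm and 3.0, 5.6, 7.2, 6.5% at 35.

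**The case against.** **The interval may not bind.** SAP 2.9.1 first accepts equivalence on CMH P > 0.05 with no margin and brings in the interval as a further measure. Protocol 9.4.6 also relies on P > 0.05, and neither document says whether one rule suffices. If P > 0.05 suffices, changing the interval alters no claim. At a true 20-point deficit and 95% control, CMH P > 0.05 occurs in about 37% of trials at 30 per arm and 31% at 35. Both results in step 4 have Pearson P > 0.05 (0.076 and 0.16). This stands as a limit on the consequence. It does not clear the interval, which is the only margin-based safeguard in the SAP and is expressly used to make a claim.

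**The zero-width case changes no decision.** True: the score limits are also inside +/-20, and 100% response would be visible in the tables. The interval is still wrong for its stated purpose of measuring the margin.

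**The inflation rests on an unstated rate.** True. Text after the sample-size statement in SAP 2.5 is redacted and may hold one. Counting missing outcomes as failures also moves observed rates away from the ceiling.

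**The effect is small near full enrolment.** At 35 per arm and 95% control it is 6.1% against 4.6%. With both true rates at 98%, the two methods disagree in 2.1% of trials at 30 per arm and 0.3% at 35.

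**The proposed method was not itself evaluated.** The score error rates are unstratified. For 27/30 vs 30/30, stratifying moves the lower limit only to -22.8, but error rates and power of the stratified version were not calculated.

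**Conclusion.** The concern holds. That the interval collapses when all respond follows directly from the specified method. The excess false-claim rate is conditional on a control rate of about 95% or more. It is modest at 95% (about 6% to 7% against 5%), reaches 12.3% only at 30 per arm with 100% control, is essentially gone at about 90%, and reverses below that. At 35 per arm with 100% control the score interval gives no improvement. These figures assume a true 20-point deficit and mainly an absolute margin; the relative reading also exceeds 5% from about 95%.

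This should be corrected, with medium confidence in its practical weight because the response rate is unknown and the parallel P > 0.05 rule may override the interval.

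**What to change.** In SAP 2.9.1, replace the ANOVA intervals with wording such as:

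> The difference in proportions and its two-sided 90% and 95% confidence intervals will be calculated by the Miettinen-Nurminen (score) method, stratified by study eye side. If all subjects respond, the P value will be reported as not estimable and the confidence interval will still be reported.

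Newcombe's interval is a workable alternative: at control 100/98/95/90% its false-claim rates are 4.4, 5.2, 5.0, 4.9% at 30 per arm and 6.1, 4.7, 5.2, 5.3% at 35. A Wald interval should not be used, since it also has zero width at 100%. The SAP should also say whether the 20% is absolute points or relative to the reference rate.

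The cost is SAP wording and a different procedure call, with no new data. The interval is somewhat wider, so a claim is less likely when the arms are truly equal:
- Both rates 95%: 84% instead of 92% at 30 per arm; 89% instead of 93% at 35.
- Both rates 90%: 56% instead of 66% at 30 per arm; 66% instead of 73% at 35.

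At 95% part of that loss is the ANOVA interval's excess claims being removed. At 90%, where ANOVA is close to nominal, it is mostly a real loss. The P > 0.05 acceptance rule needs its own correction.

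### One two-sided rule serves both equivalence and non-inferiority, so AG-920 can lose the non-inferiority claim when it is better by enough that the upper 90% limit exceeds +20%

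*SAP*

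**What the plan says.** SAP 2.9.1 (Primary efficacy analysis) takes the difference in the proportion with adequate anesthesia from a two-way ANOVA on the 0/1 outcome, with treatment and study eye side as effects. It then sets the decision rule: the 90% interval for that difference has to fall "within +/-20% of the reference treatment will be employed to claim the therapeutic equivalence or non-inferiority of AG-920 to Proparacaine". The readable text of both documents contains no separate rule based on the lower limit.

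Other passages bear on the rule:

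- Protocol 9.4.1 fixes the direction as AG-920 minus Proparacaine ("Topical Ophthalmic Solution – Proparacaine, with the 95% CI of the difference being reported"), so positive values favour AG-920.
- SAP 2.5 says the aim is a comparison with an active control, "rather than testing for superiority against the latter".
- SAP 2.9.1 also treats P > 0.05 as "indicating the therapeutic equivalence of AG-920 to Proparacaine without reference to a pre-defined non-inferiority margin".
- Protocol 9.4.6 has the P > 0.05 route for equivalence ("then the therapeutical equivalence of AG-920 to the Proparacaine will be claimed, without reference to a pre-defined non-inferiority margin"). It adds that "The 95% CI of the difference in response rates will be reported to measure the extend or margin of the efficacy equivalence". It has no ±20% rule and no non-inferiority claim.

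**The concern.** Equivalence asks whether AG-920 is neither much worse nor much better than Proparacaine, so both limits matter. Non-inferiority asks only whether it is not much worse, so a high upper limit is no evidence against it. The SAP attaches one two-sided condition to both claims. A favourable result can then be refused the weaker, one-sided claim because the difference in AG-920's favour may be large.

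This concerns the only efficacy endpoint, since SAP 2.6.2 and 2.9.2 define no secondary one. Treatment is masked to subjects and guardians only (Protocol 3.5, SAP 2.4). Dropping the upper limit after a favourable result would therefore look like a choice made with the data in view. The defect also survives any decision on whether the P-value rule or the interval rule governs, because it lies inside the interval rule.

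**Working it through.** **Inputs from the documents.** A 90% CI and a ±20% margin (SAP 2.9.1); the direction of the difference (Protocol 9.4.1); 1:1 allocation, about 70 randomized for 60 evaluable, roughly 30 per group (Protocol Summary, 9.2). The sample size cannot be re-derived. Protocol 9.2 says it follows regulatory direction, and no rates, power or design margin appear in the readable text (part of SAP 2.5 is redacted).

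**Assumptions.** True response rates as shown below. Eye side is balanced and has no effect. The 20% is absolute points unless stated.

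**Interval.** With a responders on AG-920, b on Proparacaine and n per arm:

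- d = (a − b)/n
- SSE = a(n − a)/n + b(n − b)/n
- s² = SSE/(2n − 3), SE = √(2s²/n)
- 90% CI = d ± t(0.95; 2n − 3) × SE

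**Worked case, 30/30 against 26/30.** d = 4/30 = 0.133. SSE = 0 + 26×4/30 = 3.467. s² = 3.467/57 = 0.0608. SE = √(2×0.0608/30) = 0.0637. With t = 1.672 the half-width is 0.106. The CI is +2.7 to +24.0 points: the lower limit is above zero, yet the rule fails.

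**Other results on the same formula:**

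| AG-920 vs Proparacaine | 90% CI (points) | Rule as written |
|---|---|---|
| 35/35 vs 31/35 | +2.3 to +20.6 | fails, upper limit only |
| 29/30 vs 26/30 | −2.0 to +22.0 | fails, upper limit only |
| 25/30 vs 24/30 | −13.8 to +20.5 | fails, upper limit only |
| 30/30 vs 27/30 | +0.6 to +19.4 | passes |
| 29/30 vs 27/30 | −4.3 to +17.6 | passes |

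**How often.** All outcome pairs for 30 per arm were enumerated with exact binomial weights:

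| True rates AG-920/Proparacaine (assumed) | Both limits inside ±20 | Lower limit above −20 | Fails on upper limit alone |
|---|---|---|---|
| 90/80% | 25.8% | 94.8% | 69.0% |
| 95/85% | 41.5% | 99.1% | 57.6% |
| 95/90% | 71.4% | 98.1% | 26.7% |
| 90/90% | 66.4% | 83.2% | 16.8% |
| 98/95% | 94.3% | 99.8% | 5.5% |
| 99/97% | 98.8% | 100.0% | 1.2% |

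The last column is the third minus the second. The 90/90 row shows that AG-920 need not be truly better for the rule to withhold the claim.

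**Relative reading.** If 20% means 20% of the observed Proparacaine rate, the last column rises to 78% at 90/80, 39% at 95/90 and 28% at 90/90. The rise is not universal: at 80/70 it goes from 77% to 69%, because the tighter lower bound also fails more often.

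**The case against.** A reader might infer that AG-920 loses the claim whenever it works better. The rule does not do that. It fails a better AG-920 only when the upper limit passes +20%. At 30 per arm on the absolute reading, no better AG-920 result can fail once Proparacaine reaches 27/30. The one hint about the comparator's rate is that the Introduction calls its surface anesthesia excellent. This gives no figure, but it points toward the rows where the loss is small.

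A reader might also infer that the trial would then fail its only efficacy claim. That does not follow, because the P > 0.05 route to equivalence stands beside the interval rule. With 29/30 against 26/30, P = 0.16, so that route grants equivalence while the interval rule refuses it. The route does not repair the point, however. It offers equivalence only, and it too denies the claim when AG-920 is significantly better (30/30 against 26/30, P = 0.038).

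Two further objections stand. The error is conservative: it withholds a claim and does not create a false one, and both intervals will be reported, so readers can see the lower limit. And the protocol names only equivalence, for which a two-sided rule is right, so the fault may be no more than a few surplus words in the SAP.

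**Conclusion.** The point holds in this limited form: SAP 2.9.1 applies an equivalence condition to a non-inferiority claim, so a sufficiently favourable result can be refused non-inferiority on the upper limit alone. With 30 per arm and 20 absolute points, the share of trials affected runs from about 69% (90/80) to about 1% (99/97). These shares depend on assumed response rates, a balanced eye side without effect, and the absolute reading. No single row is a best estimate, because the readable text gives no rate. That the wording assigns a two-sided rule to a one-sided claim depends on none of these assumptions.

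**What to change.** In SAP 2.9.1, split the rule:

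- Claim non-inferiority when the lower limit of the stated CI for AG-920 minus Proparacaine is above the negative margin. Do not use the upper limit.
- Claim equivalence only when both limits are inside the margin.
- Name which claim is primary. If only equivalence is intended, as in Protocol 9.4.6, delete *or non-inferiority* instead.
- Say whether 20% is absolute points or relative to the Proparacaine rate.
- Put the same rule in Protocol 9.4.6.

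This is a wording change to settle before outcome data are reviewed. It needs no extra subjects or data.

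Using the 95% CI for the lower limit, in line with Protocol 9.4.1 ("Hypothesis testing, unless otherwise indicated, will be performed at a two-sided 0.05 significance level"), is a separate and optional choice with a trade-off. Against the current two-sided 90% rule at 30 per arm, the false-claim rate at true rates of 75% (AG-920) and 95% (Proparacaine) falls from 7.0% to 3.7%. The chance of success rises from 66.4% to 71.9% when both true rates are 90%, but it falls from 71.4% to 60.9% when AG-920 is slightly worse (90% against 95%).
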